2. BACKGROUND

2.1 Study Disease

EGFR mutant NSCLC represents a genomically distinct subgroup of lung cancer. These patients have been demonstrated in multiple large randomized trials to exhibit high ORR and progression-free survival when treated with first-generation EGFR kinase inhibitors such as erlotinib.¹⁻⁵ However, these agents are minimally active in EGFR wild-type patients. The use of these agents is thus largely restricted to patients possessing an EGFR sensitizing mutation. The timely initiation of these treatments hinges upon accurately and rapidly detecting these predictive EGFR mutations. The only means of detecting these mutations currently is through genotyping performed upon a tissue biopsy – an invasive and often time consuming process.

[figure not shown]
The development of newer genotype-directed therapies in resistant disease has also led to an increased need for post-treatment tissue biopsies in order to allow clinical trial enrollment.^{6,7} A patient with advanced NSCLC may thus undergo multiple tissue biopsies during the course of their disease with the availability of tumor tissue representing a key limitation. The need for tissue biopsies invariably leads to both a delay in the initiation of erlotinib therapy in *EGFR* mutant patients as well as standard chemotherapy or potential clinical trial enrolment in *EGFR* wild type patients – in extreme cases patients may be unable to access certain treatments or trials if a biopsy fails or is not technically feasible.

2.2 Plasma Genotyping

Plasma genotyping is a promising and evolving analytic method which allows for noninvasive tumor genotyping to be performed on patient plasma samples. Cell-free DNA (cfDNA) can be readily isolated from these samples and contains a portion of tumor derived DNA. This cfDNA may then be evaluated using various genotyping assays in order to detect the presence of a potentially targetable genomic alteration. The potential of this technology has been demonstrated in various early studies across multiple tumor types. These have demonstrated that highly sensitive qualitative genotyping assays are able to detect mutations in cfDNA reflecting underlying mutations in a patient's tumor.⁸⁻¹⁰ However, interpretation of these highly sensitive qualitative assays is marred by false positives caused by the detection of clinically insignificant levels of mutations in cfDNA.¹¹ As such, no plasma genotyping assays have yet entered routine clinical use. Competing assays which analyze circulating tumor cells initially garnered similar enthusiasm, but have been slowed by significant technical challenges.¹²

2.3 Study Assay

Our group has developed a novel assay utilizing droplet digital PCR (ddPCR) technology to perform noninvasive and quantitative genotyping on cfDNA collected from plasma samples. This assay utilizes ddPCR to emulsify collected cfDNA from patient plasma into approximately 20 000 droplets that undergo individualized PCR reactions and analysis allowing for the quantification of mutant versus wildtype copy number [Figure 1].¹³ Previously published work by our group has demonstrated the technical feasibility and accuracy of this plasma genotyping assay for detecting both activating and resistance mutations in *EGFR* (exon 19 del, L858R and T790M) as well as *KRAS* mutations in NSCLC patients.¹³ This assay is both highly sensitive and quantitative which creates unique advantages over previous plasma genotyping methods. We have demonstrated that the quantitative nature of this assay combined with quality control methods can minimize the false positive results that have plagued earlier assays. The quantitative nature of this assay may also be exploited to allow prediction of early treatment failure as well as the development of treatment resistance.

from a plasma specimen and emulsified with oil into ~20,000 droplets, each containing approximately 0-1 molecules of target DNA. PCR is performed to endpoint in each droplet. These droplets are run through a flow cytometer, where droplets containing mutant and wildtype DNA emit different colored signals. The count of these signals allows quant bication of sole allows are recepted as a through a flow cytometer.

Protocol: 16-093: Rapid Initiation of Erlotinib for Advanced NSCLC Using Genotyping of Cell-free Plasma DNA

Version date: February 15, 2017

Following initial validation of this assay in a small group of patients as described above, we retrospectively examined this assay in a larger group of metastatic NSCLC patients with EGFR sensitizing mutations (exon 19 del, L858R) and acquired resistance to EGFR kinase inhibitors. This study compared the test characteristics of our ddPCR-based plasma genotyping assay for the detection of both EGFR sensitizing and the T790M acquired resistance mutation in a cohort of 41 patients with advanced NSCLC who had undergone re-biopsy and standard tissue genotyping for comparison. This revealed 70% assay sensitivity for detection of EGFR T790M and a 93% assay specificity to T790M. In addition, a subset of 15 of these patients underwent serial plasma genotyping after beginning a new line of systemic/targeted therapy. This subset of patients underwent baseline plasma genotyping followed by repeat testing with each treatment cycle. Patients with a partial response to treatment uniformly exhibited decreased levels of *EGFR* cfDNA over time whereas patients without response exhibited stable or increased levels [Figure 2].¹⁴ These data indicate that this assay may also predict treatment outcome as early as 4 weeks after initiating treatment – potentially allowing early treatment modification.

We have subsequently initiated a prospective study of ddPCR-based plasma genotyping in a planned cohort of 340 NSCLC patients in order to assess its ability to accurately detect *EGFR* sensitizing (exon 19 del, L858R), T790M and *KRAS* G12X mutations. These patients include newly diagnosed patients, those with acquired resistance to kinase inhibitors and those undergoing a new line of subsequent treatment. The aims of this study include assessing both test characteristics compared to gold standard tissue genotyping performed on a biopsy specimen as well as correlating change in detectable levels of mutations

during treatment with radiographic response through serial blood testing. This study has accrued 250 patients thus far. Median TAT for plasma ddPCR is 3 days (range 1-5). Specificity of plasma ddPCR is 99% for 19 del/L858R (94/95) and 100% for *KRAS* (82/82), but lower for T790M at resistance (81%, 22/27). Sensitivity

[figure not shown]

Figure 2: change in *EGFR* mutation copy number in advanced NSCLC patients with (A) and without (B) a partial radiographic response after initiating a new line of therapy (PR – partial response, SD – stable disease, PD – progressive disease per RECIST 1.1).

[figure not shown]

Figure 3: log-fold change in mutation copy number in advanced NSCLC patients correlates with radiographic response in patients treated with both standard chemotherapy and kinase inhibitors (per RECIST 1.1).

of plasma ddPCR is 75% for 19 del/L858R (73/97) and 73% for T790M (30/41) but lower for *KRAS* (62%, 16/26).

Taken together, these previous studies indicate that ddPCR-based plasma genotyping using our validated assay is able to detect *EGFR* sensitizing mutations (exon 19 del, L858R) in metastatic NSCLC with a

high degree of specificity and acceptable sensitivity. A positive result from this assay is thus highly specific for the presence of an *EGFR* mutation and clinically actionable given the very low likelihood of false positive results.

2.4 Study Agent

Erlotinib is an oral tyrosine kinase inhibitor which specifically inhibits the epidermal growth factor receptor (EGFR) through non-covalent competitive binding to the ATP-binding site of the receptor. It preferentially inhibits the activity of EGFR possessing activating mutations in the kinase domain. This agent is FDA approved for the treatment of advanced NSCLC possessing an activating mutation in the EGFR kinase domain (e.g. *EGFR* exon 19 del, L858R).^{1,2}

Erlotinib is a well tolerated oral medication with a favorable side-effect profile. The most frequent adverse events noted in previous studies include diarrhea, acneiform rash and changes in skin/hair. Rare but serious adverse events including pneumonitis and hepatotoxicity have also been reported in previous studies.^{1,2}

Erlotinib has been previously demonstrated in multiple phase III trials to exhibit similar overall survival benefit to first-line platinum-doublet chemotherapy in advanced NSCLC possessing an *EGFR* sensitizing mutation (exon 19 del/L858R). The objective response rate (ORR) in these trials has been approximately 70% with a disease control rate approaching 90% in most trials.^{1,2} Given this efficacy data and its favorable toxicity profile, erlotinib has been adopted as the standard initial treatment of advanced *EGFR* mutant NSCLC. The standard initial dosing of erlotinib is 150 mg po daily.

2.5 Rationale

This rapid and accurate ddPCR-based plasma genotyping assay combined with immediate treatment with erlotinib in *EGFR* mutant (exon 19 del/L858R) patients has the potential to both expedite appropriate therapy as well as avoid missed treatment opportunities in patients where tissue biopsies are delayed or not feasible. We have designed a prospective single-arm phase II study to evaluate a novel treatment strategy employing rapid plasma genotyping followed by immediate erlotinib treatment in *EGFR* mutant patients (exon 19 del/L858R) compared with standard genotyping followed by treatment. This study would specifically evaluate this novel treatment strategy compared with standard treatment with respect to the speed with which erlotinib therapy is initiated, the appropriateness of the first-line treatment initiated and overall response rate.

3. PARTICIPANT SELECTION

3.1 Eligibility Criteria

Participants must meet the following screening criteria in order to enroll and undergo plasma genotyping on this study:

- 3.1.1 Histologically or cytologically confirmed metastatic NSCLC including recurrent disease
- 3.1.2 *EGFR* genotype must not be known. However, pending *EGFR* tumor genotyping is allowed.
 - 3.1.2.1 Participants with positive or pending EGFR mutation on plasma genotyping performed at the central lab are eligible for enrollment, and will not need to repeat initial plasma genotyping on study.

CONFIDENTIAL

3.1.3 Tissue must be available for genotyping or biopsy planned to obtain tissue for genotyping. Biopsy requirement may be waived if not technically feasible and plasma genotyping reveals an eligible *EGFR* mutation (exon 19 del/L858R). Determination of technical feasibility must be made independently of plasma genotyping results.

- 3.1.4 Participants must possess at least two of the following clinical characteristics which enrich for *EGFR* mutations:
 - smoked less than 10 pack years
 - Asian race
 - Adenocarcinoma (including adenosquamous carcinoma) on histology or cytology.
- 3.1.5 Participants must have measurable disease with at least one lesion that can be accurately measured in longest dimension as >2 cm with conventional imaging techniques or >1 cm with a spiral CT scan per RECIST v1.1.
- 3.1.6 Participants must have progressive, advanced cancer as defined by one of the following:
 - Newly diagnosed, untreated advanced disease
 - Newly diagnosed, untreated metastatic recurrence of earlier stage disease (previous treatment of early stage disease allowed).
 - Clinical determination of progressive disease on previous systemic therapy as evidenced by plan to change treatment. Any number of prior therapies are acceptable excluding previous EGFR kinase inhibitors.
- 3.1.7 Age 18 years or older.
- 3.1.8 ECOG performance status 0-2.
- 3.1.9 Participant must be able to understand and give consent to participate in the study.
- 3.1.10 Patient must be a candidate for systemic therapy with erlotinib based on clinical assessment. Patients must meet the following criteria before beginning therapy (Note: these are not required for initial study enrollment and plasma genotyping):
 - ECOG performance status of 0-2
 - Platelets >75
 - AST & ALT < 3x the upper limit of normal
 - Creatinine clearance > 30 mL/min by Cockroft-Gault
 - No other contraindication to erlotinib
 - Female participants of child-bearing age must agree to use adequate contraception (hormonal, barrier or abstinence) for the duration of the study while receiving erlotinib and undergo a pregnancy test. Any evidence or suspicion of pregnancy should be reported to the treating physician immediately.
 - Male participants must agree to use adequate contraception for the duration of the study while receiving erlotinib

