1.3 Secondary Objectives

- Determine the time from study registration to treatment initiation using a rapid plasma genotyping strategy versus standard tumor genotyping.
- Ascertain the positive predictive value and false negative rate of plasma genotyping for patients with recently diagnosed advanced NSCLC among patients with tissue available for standard genotyping.

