4.1 General Guidelines for DF/HCC Institutions

Institutions will register eligible participants in the Clinical Trials Management System (CTMS) OnCore. Registrations must occur prior to the initiation of protocol therapy. Any participant not registered to the protocol before protocol therapy begins will be considered ineligible and registration will be denied.

An investigator will confirm eligibility criteria and a member of the study team will complete the protocol-specific eligibility checklist.

Registration on the Initial Registration arm (Step 1) occurs at the time of initial plasma genotyping. Registration to the erlotinib treatment arm (Step 2) takes place once positive EGFR mutation status is confirmed. Following registration for erlotinib treatment, participants may begin protocol therapy. Issues that would cause treatment delays should be discussed with the Overall Principal Investigator (PI). If a participant does not receive protocol therapy following registration, the participant's registration on the study must be canceled. Registration cancellations must be made in OnCore as soon as possible.

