^dRepeat plasma genotyping not required if positive or pending at the central lab at time of registration.

^eRegistration to the Initial Registration arm (Step 1) occurs at the time of initial plasma genotyping. ^fRegistration to the erlotinib treatment arm (Step 2) occurs once positive EGFR mutation status is confirmed.

^g Required for female participants of child-bearing age.

*Baseline scan and initial 4 follow-up scans will undergo objective assessment for response; subsequent scans will be used for clinical assessment of progression but will not undergo objective measurement. Participants positive for an EGFR mutation by plasma genotyping but negative by tissue genotyping will undergo an interim CT scan at 4 weeks after initiating erlotinib to confirm response.

All assessments must be performed prior to administration of any study medication. All study assessments and medications should be administered within \pm 7 calendar days of the protocol-specified date, unless otherwise noted. Follow-up tumor assessments may be made within \pm 7 calendar days of the protocol-specified date.

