15.4 Analysis of Secondary Endpoints

From a total of 100 NSCLC patients studied, we estimate that 30 will have an *EGFR* sensitizing mutation (exon 19 del/L858R), respectively, based upon prior prevalence data at our institution. Concordance between tumor and plasma genotyping results will be calculated using a Cohen's kappa. The potential clinical value of the ddPCR genotyping assay will be estimated using:

• Positive predictive value (PPV): To be clinically useful, the PPV must exceed 90% for the plasma assays for *EGFR* and *KRAS* mutations.

• Sensitivity: The sensitivity of each assay must exceed 70% to have clinical value.

• Efficiency: The turnaround time (TAT) between ordering the plasma genotyping and obtaining the result will be compared to the TAT for tumor genotyping. We will compute the turnaround time for each, and compare them using the Wilcoxon-test. To have maximal clinical value, the median TAT for plasma genotyping must be less than 3 days.

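### Patients already known to be plasma-positive can register without re-testing and are pooled into the sensitivity estimate, which biases it upward when tissue verification is equal

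*Combined protocol and SAP*

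**What the plan says.** Section 3.1.2 requires that EGFR genotype be unknown at entry. Section 3.1.2.1 then makes an exception: "Participants with positive or pending EGFR mutation on plasma genotyping performed at the central lab are eligible for enrollment", and these patients do not repeat the initial plasma test. Footnote d of the section 10 calendar repeats the waiver: "plasma genotyping not required if positive or pending at the central lab at time of registration". Neither place mentions a known negative result.

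Section 1.3 sets as a secondary objective the positive predictive value and the "false negative rate of plasma genotyping for patients with recently diagnosed advanced NSCLC among patients with tissue available for standard genotyping". Section 15.4 plans Cohen's kappa, a PPV bar of 90% and a sensitivity bar: "The sensitivity of each assay must exceed 70% to have clinical value". Nothing in 1.3, 15.4 or 15.5 excludes, separates or weights patients who registered on a known positive.

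Section 3.1.3 allows the biopsy requirement to be waived only when plasma shows an eligible mutation, although feasibility must be judged without regard to the plasma result. On timing, section 4.1 states: "Registration on the Initial Registration arm (Step 1) occurs at the time of initial plasma genotyping".

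**The concern.** Part of the sample can be selected by the result of the test under evaluation. A patient who registers because plasma was already positive, and whose tissue confirms the mutation, enters the numerator and denominator of sensitivity together. The counterpart, a mutation carrier whose plasma test was already negative, has no corresponding route in. Patients whose result is pending cause no such bias, because they register before the result is known.

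This matters because 15.4 attaches a verdict to sensitivity, and the prior estimate in section 2.3 (73/97, 75%) is only about five points above the bar. The same entrants also affect the registration-to-treatment time in 1.3. For everyone else, registration coincides with the plasma test. For a known positive the test came earlier, so its turnaround (median 3 days in section 2.3) can fall outside the measured interval.

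**Working it through.** **Inputs from the documents.** Prior sensitivity is 73/97 = 0.753 and prior specificity is 94/95 = 0.989 (section 2.3), matching the stated 75% and 99%. The exact 95% interval for 73/97 is 0.655 to 0.835. Section 15.4 expects 30 carriers per 100, a prevalence of 0.30. Section 15.2 expects about 30 plasma-positives per 100, which needs a prevalence of (0.30 − 1/95)/(73/97 − 1/95) = 0.39. Both prevalences are used.

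**Assumptions.** k is the number of tissue-confirmed known positives. The documents do not give it, so k = 1 to 10 is shown. Tissue verification is equal in plasma-positives and plasma-negatives. The 70% bar is applied to the point estimate, because 15.4 gives no interval or test.

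**Expected sensitivity.** With N other carriers and true sensitivity Se,

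Se_obs = (N × Se + k)/(N + k),

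where N = 100 × prevalence if known positives come on top of the 100, or (100 − k) × prevalence if they fill places within it. Example (prevalence 0.30, k = 5, on top): (30 × 0.7526 + 5)/35 = 27.58/35 = 0.788.

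Ranges cover both prevalences and both ways of counting:

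| k | True Se 0.753 reads | True Se 0.65 reads |
|---|---|---|
| 1 | 0.759-0.761 | 0.659-0.661 |
| 2 | 0.765-0.768 | 0.667-0.672 |
| 5 | 0.781-0.790 | 0.690-0.702 |
| 10 | 0.803-0.819 | 0.721-0.745 |

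**Chance that the point estimate exceeds 70%.** This is P[(X + k)/(N + k) > 0.70] with X ~ Bin(N, Se), averaged over N ~ Bin(100, 0.30) or Bin(100 − k, 0.30):

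| k | True Se 0.753 | True Se 0.65 |
|---|---|---|
| 0 | 0.745 | 0.283 |
| 1 | 0.782 | 0.324-0.325 |
| 2 | 0.815-0.816 | 0.367-0.370 |
| 5 | 0.896 | 0.503-0.514 |
| 10 | 0.967-0.969 | 0.716-0.745 |

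At prevalence 0.39 and true 0.65, the chance goes from 0.256 to 0.442-0.454 at k = 5. With N held fixed at a value from 26 to 34 (true 0.65), the rise at k = 5 is 0.14 to 0.31. At k = 1 or 2 it is 0.00 to 0.15, because the outcome moves in whole patients.

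**Kappa** (specificity 94/95, prevalence 0.30, Se 0.753): 0.793, 0.798, 0.803, 0.816-0.817 and 0.834-0.837 for k = 0, 1, 2, 5 and 10.

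**Offset from unequal verification.** If plasma-positives are verified at r times the rate of plasma-negatives, the bias cancels when r = N × Se/(N × Se + k). At Se 0.753 that is 0.92-0.94 for k = 2 and 0.81-0.85 for k = 5. A lower r makes the net bias downward and a higher r makes it upward.

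**The case against.** The strongest objection is size. Everything depends on k, and the documents point to a small one: section 2.2 says "no plasma genotyping assays have yet entered routine clinical use". At k = 1-2 the shift is one to two points, well inside sampling error with about 30 carriers (exact 95% interval for 23/30: 0.58 to 0.90). The one source the documents suggest is the prospective plasma cohort in section 2.3, of which it says: "This study has accrued 250 patients thus far". That source is doubtful. Those patients are compared with tissue genotyping, and a completed tissue result bars entry under 3.1.2. Any who have had an EGFR inhibitor are barred by 3.2.2. Section 2.3 also does not say that the tests were run at the central laboratory. This objection stands: k = 1-2 is easier to support than k = 5-10, and at k = 0 there is no bias.

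Second, a known plasma-negative is not expressly excluded. At 75% sensitivity a negative plasma result arguably leaves the genotype unknown, so such a patient might enter by the ordinary route and be re-tested. That is a fair reading, but it removes the bias only if known negatives enter in proportion, and nothing in the plan brings that about.

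Third, the biopsy waiver may leave plasma-positives less often verified, which pulls sensitivity down. This also stands, and it is why the claim is limited to equal verification. Two uncontrolled biases that might cancel are a reason to show both.

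Fourth, sensitivity is a secondary criterion with no formal test, and the true value of 0.65 used as illustration lies just below the 95% interval. Both points are correct and limit the stakes. The turnaround comparison in 15.4 runs from order to result, so it does not depend on registration date.

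**Conclusion.** The concern holds. As written, the plan pools patients selected on a positive plasma result into an estimate of that test's sensitivity, with no counterpart for known negatives. At equal tissue verification this raises sensitivity, lowers the false-negative rate and, over the range computed, raises kappa. The net direction in the trial is not established, because verification may differ by plasma result.

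At the documented sensitivity the consequence is an inflated estimate (by about 1-2 points for k = 1-2 and 3-4 points for k = 5), with no change in the expected verdict. The verdict is at risk only if true sensitivity is near or below the lower end of the interval for 73/97. These sizes rest on an assumed k, on prevalence of 0.30 or 0.39 and, for the pass probabilities, on a point-estimate reading of the 70% bar. PPV is little affected, and the rule of 17 responses in 30 is unaffected. The change is worth making because it is cheap and because the 70% bar is stated in the plan. Confidence is medium.

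**What to change.** Record plasma status at registration as unknown, pending or known positive. In 15.4, define the main estimates of sensitivity, false-negative rate and kappa in patients whose plasma result was not known at registration (unknown and pending together). Report the pooled estimates as a sensitivity analysis. Beside both, show the number of patients without a tissue result, split by plasma result, so that unequal verification is visible. Keep known positives in the response-rate and PPV analyses. In the registration-to-treatment time of 1.3, leave them out or report them separately.

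The cost is one registration field and a few lines of analysis wording. The status might also be derived from result and registration dates if both are captured. The statistical cost is a slightly smaller denominator for sensitivity. At 30% prevalence and k = 5, it is about 30 carriers rather than 35 if known positives come on top of the 100, or about 28.5 rather than 33.5 if they fill places within it. No patient is excluded from the trial.
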